### **Trauma History and PTSD**

- Clinician Administered PTSD Scale (CAPS) (Weathers, Keane, & Davidson, 2001): The CAPS for DSM-5 is a 30-item structured diagnostic interview and gold standard for assessing PTSD (Weathers et al., 2014). The CAPS has excellent psychometric properties and diagnostic efficiency (Weathers et al., 2001). The CAPS-5 was revised to accommodate changes made in DSM-5, reduce administration time, and facilitate scoring procedures.
- PTSD Checklist (PCL-5) (Weathers et al., 2013): The PCL-5 is a 20-item self-report measure. The PCL-5 is similar in form to the PTSD Checklist (PCL) based on the DSM-5 (Weathers et al., 1993), which has excellent psychometric characteristics for screening and as a secondary indicator of PTSD symptom severity (McDonald & Calhoun, 2010).
- Life Events Checklist for DSM-5 (LEC-5) (Weathers et al., 2013): The LEC-5 assesses lifetime exposure to trauma. It includes the list of 16 different events from the original LEC. In addition, two items screen for military sexual trauma. The primary addition to the LEC-5 is a category involving occupational exposure (e.g., paramedic, police, or other first responder).
- Childhood Trauma Questionnaire-Short Form (CTQ-SF) (Bernstein et al., 2003): The CTQ is a 28-item self-administered inventory that assesses childhood abuse and neglect. The CTQ-SF contains subscales including physical, sexual, and emotional abuse, and physical and emotional neglect.

## Protocol: Glial Regulators for Testing Comorbid Posttraumatic Stress Disorder and Substance Use Disorders

- Coping Inventory for Stressful Situations: Situation Specific Coping (CISS: SCC): Assesses an individual's coping preferences for a designated event (Endler & Parker, 1990).

### **Depression and Suicidality**

- Beck Depression Inventory-II (BDI-II); Beck et al., 1996): The 21-item BDI-II is one of the most widely used instruments for measuring the severity of depressive symptoms. Total scores reflect minimal (0-13), mild (14-19), moderate (20-28), or major depressive symptoms (29-63).
- Columbia Suicide Severity Rating Scale (C-SSRS); Posner et al., 2007): The C-SSRS will be used to assess past/lifetime and current suicide ideation. It will be administered at baseline (for study eligibility), week 4 and week 8, and additionally as needed during the trial to monitor subject safety.

### **Associated Areas of Functioning**

- Deployment Risk and Resiliency Inventory-2 (DRRI-2): The DRRI-2 (Vogt et al., 2012) is a suite of 17 individual scales that assess key deployment-related risk and resilience factors with demonstrated implications for Veterans' long-term health. The following subscales will be used to assess deployment factors: Combat Experiences. We will use the Post-Deployment Life Events and Support scales to evaluate post-deployment factors for Veterans.
- CNS Vital Signs Cognitive Testing: A battery of two tests (Stroop & Shifting Attention) will assess neurocognitive functions.

**Compensation:** Participants will be compensated \$50 for the baseline visit, \$50 for each imaging visit, \$40 for each completed weekly visit, and \$75 for completing each of the follow-up visits. They will be given a \$25 bonus if the baseline/first visit is attended as scheduled. Participants who previously consented to the optional neuropeptide Y will receive \$15 compensation for completing the second blood draw. Thus, participants may receive up to \$755 for completing all visits. Compensation is available in the form of cash, gift card, or check.

Telehealth participants will be offered compensation for travel to and from the three mandatory in-person visits (Baseline, Week 4, & Week 8).

**Neuroimaging Component:** Given the severe negative outcomes associated with co-occurring AUD/SUD and PTSD and lack of effective treatments, investigation of the neural circuitry and neurochemistry underlying AUD/SUD/PTSD and involved in positive therapeutic response could be important in guiding future treatment development studies. To that end, fMRI and H-MRS data will be acquired at baseline and end of treatment on a subset (n=40) of participants to examine (a) glutamate concentrations, (b) resting state connectivity, and (c) response to alcohol/drug, trauma, and neutral cues. Scans will be conducted at the MUSC Center for Biomedical Imaging.

The neuroimaging component will involve three visits, each lasting 60-90 minutes. During visit 1, we will develop the personalized imagery scripts for alcohol/drug, trauma, and neutral cues. During visit 2 (pre-treatment) and visit 3 (end of treatment), we will conduct the fMRI and H-MRS scanning procedures. Imagery scripts will be similar to those developed according to standardized procedures (Sinha & Li, 2007) and employed in our ongoing research.

Upon arrival to the imaging facility (Center for Biomedical Imaging), participants will first participate in a mock scanning session to acclimate to the MRI scanner and to practice using the joystick before completing the actual MRI scan. After mock scanning, participants will be screened for metal using a handheld metal detector. Trained staff will position individuals on the scanner bed with foam padding placed around their head to prevent motion. Participants will wear ear buds to listen to the audio-recorded scripts. For co-registration and normalization of functional images, a high resolution T1-weighted MPRAGE anatomical image will be acquired with the following parameters: TR = 2300ms, TE = 2.26ms, flip angle = 8°, field of view = 256mm, slice thickness 1.0mm. The scanning planes will be oriented parallel to the anterior commissure–posterior commissure line. The ACC voxel for H-MRS will be placed on midsagittal T1-weighted images, anterior to the genu of the corpus callosum, with the ventral edge of the voxel aligned with the dorsal edge of the genu and a voxel size of 3 x 2.5 x 2.5cm.

## Protocol: Glial Regulators for Testing Comorbid Posttraumatic Stress Disorder and Substance Use Disorders

Following auto-shimming, single-voxel water-suppressed  $^1\text{H}$ -MRS spectra will be acquired using a Point Resolved Spectroscopy (PRESS) sequence: Repetition Time (RT) = 2000ms; Echo Time (TE) = 40ms; number of averages = 128; an unsuppressed water spectrum will be co-acquired (TE = 40ms, number of averages = 16), scaled for partial volume effects and relaxation, and used as a concentration reference (Mullins et al., 2008).

Participants will be asked to relax and keep their eyes opened and fixed on a cross-hair for two six-minute runs while resting state data are collected. Following this, participants will be exposed to alcohol/drug, trauma and neutral cues, which will be audio recorded descriptions of the most recent time they used alcohol/drug, details of a traumatic event, and details about a relaxing event.

We will use a block design consisting of a single run in which 4 task blocks alternate with rest blocks. The 4 task blocks consist of a neutral cue followed by a trauma cue followed by a neutral cue then an alcohol/drug cue. To minimize potential carry-over effects, the order of task blocks will be counterbalanced so that half of the subjects in the placebo group and half of the subjects in the NAC group are exposed to the alcohol/drug cue first and the remaining participants in each group are exposed to the trauma cue first. This order will be repeated at the end of treatment scan. T2\*-weighted gradient-echo planar images (EPI) will be acquired with the following parameters: TR = 1100ms, TE = 30ms, flip angle =  $65^\circ$ , matrix 64 x 64, field of view = 192mm, slice thickness = 3.0mm, with 48 slices to cover the entire brain.

**Statistical Analyses:** Baseline clinical and demographic characteristics will be collected and contrasts performed between treatment groups. Baseline characteristics found to be significantly associated with primary outcome measures will be included as covariates in the analyses. In general, less than 10% missing data have little impact on power and do not introduce bias, regardless of the missing data mechanism. If the percent missing data are greater than 10%, propensity score methods will be used for data imputation.

We plan to use REDCap for data capture and management. REDCap (Research Electronic Data Capture) is a software toolset and workflow methodology for electronic collection and management of research and clinical trial data (Harris et al., 2008; Harris et al., 2007). REDCap provides secure, web-based flexible applications, including real time validation rules with automated data type and range checks at the time of entry. Exports are made available for several statistical packages including SPSS, SAS, SATA, R and Microsoft Excel.

**Power and Sample Size Estimation.** It is expected that subjects treated with NAC, as compared to placebo, will exhibit significantly lower PTSD symptoms and craving at week 8. The effect sizes for these analyses ( $d = 1.27$ ,  $d = 1.03$ , respectively) are based on our PoP data. A sample size of 26 would provide power ( $1-\beta$ ) of .80 to detect a large effect size with a Type 1 error protection level of .05 (Cohen, 1988). It is expected that NAC, as compared to placebo, will exhibit significantly lower AUD/SUD severity at week 8. To date, no published studies have examined NAC for the treatment of AUD. Assuming a medium effect size ( $d = .2$ ), with a Type 1 error protection level of .05 and  $(1-\beta) = .80$ , a total sample of 58 would be required. Recent unpublished pilot data conducted by our group examining the effects of NAC vs. placebo on standard number of drinks among patients with cocaine dependence and comorbid AUD ( $n=28$ ) found a statistically significant treatment group effect. With regard to neuroimaging, a recent study of 29 individuals (PTSD=14, controls=15) observed significant differences in PFC-AMY resting state connectivity (Sripada et al., 2012). The effect size for this difference was 0.8 (Cohen's  $d$ ). Thus, power ( $1-\beta$ ) reaches .80 with a total sample size of  $N=26$  (two-tailed,  $\alpha = .05$ ). Another study of 45 cocaine-dependent individuals showed that lower PFC-AMY connectivity at baseline predicted relapse (McHugh et al., 2014). The effect size for this reduction was 1.0. Thus, power ( $1-\beta$ ) reaches .80 with  $N=34$  subjects (two-tailed,  $\alpha = .05$ ).

**Hypotheses:** The hypotheses and statistical approaches for testing each hypothesis are listed below.

Hypothesis 1: NAC treatment will result in significantly greater reduction in AUD/SUD severity and craving, as compared to placebo. To test this hypothesis, a mixed effects modeling framework will be specified with the

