**Table 1. Assessment Instruments and Timeline**

Instrument	Baseline	Medication Initiation	Medication and Symptom Monitoring								Follow Up
	Weeks → -1	0	1	2	3	4	5	6	7	8	1 & 3 Mth
Demographic Data	X										
History and Physical Examination	X										
MINI Diagnostic Interviews	X										
Concurrent Medications Form	X	X	X	X	X	X	X	X	X	X	X
Vital Signs	X					X				X	
Medication Log		X	X	X	X	X	X	X	X	X	
Urine Pregnancy Test for Females	X					X				X	
Urine Drug Screen: UDS	X					X				X	X
Riboflavin Test		X				X				X	
Adverse Events		X	X	X	X	X	X	X	X	X	X
Breathalyzer/Saliva BAC Tests	X	X	X	X	X	X	X	X	X	X	X
Timeline Follow- Back: TLFB	X	X	X	X	X	X	X	X	X	X	X
CIWA-AR	X										
Visual Analog Scales; VAS	X	X	X	X	X	X	X	X	X	X	X
Obsessive Compulsive Drinking Scale: OCDS	X	X	X	X	X	X	X	X	X	X	X
Ethyl glucuronide (EtG)		X				X				X	X
Clinician Administered PTSD Scale: CAPS-5	X					X				X	X
PTSD Checklist: PCL-5	X		X	X	X	X	X	X	X	X	X
Life Events Checklist: LEC-5	X										
Childhood Trauma Questionnaire: CTQ-SF	X										
Beck Depression Inventory-II: BDI-II	X		X	X	X	X	X	X	X	X	X
Deployment Risk & Resiliency Inventory-2	X										
Columbia Suicide Severity Rating Scale	X					X				X	X
Penetration of the Blind Questionnaire										X	
AUDIT	X										
Cognitive Testing		X				X				X	
Blame Questionnaire	X									X	
Fagerstrom	X										
Coping Inventory	X									X	
Visual Analog Scale: VAS - fMRI	X									X	
History of Head Injuries BL	X										
History of Head Injuries FU										X	
Satisfaction Questionnaire										X	X
Treatment Services Review	X	X	X	X	X	X	X	X	X	X	X
Neuroimaging Procedures	■										■
Cognitive Behavioral Therapy: CBT			◆	◆	◆	◆	◆	◆	◆	◆	

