## Protocol: Glial Regulators for Testing Comorbid Posttraumatic Stress Disorder and Substance Use Disorders

total number of standard drinks consumed and the OCDS total score as the primary outcomes. A Poisson distribution will be assumed with a logarithm link function to assess the effects of NAC treatment. Data collected in substance abuse studies often contain a preponderance of zeros, and these zeros in the distribution can be considered sampling zeros in the Poisson process (Bandyopadhyay et al., 2011). If this excess is present in the distribution, two-part Hurdle models (Poisson and NB) will be explored (Cragg et al., 1971). The hurdle part of the model will allow us to estimate the probability of abstinence during the study period (as an odds ratio) while the Poisson/NB portion will allow for the assessment of the risk of an increase in using days beyond zero during the study period (as a risk ratio). Baseline alcohol/substance use and craving will be included in pertinent models as covariates. Additional alcohol/substance use outcomes will be assessed: change in percent drinking days, percent heavy drinking days, EtG, and VAS craving levels.

Hypothesis 2: NAC treatment will result in significantly greater reduction in PTSD severity (CAPS-5) as compared to placebo. To test this hypothesis, generalized linear mixed effects regression models with a Gaussian distribution will be developed to assess group differences while adjusting for baseline CAPS-5 scores. Assumptions of residual normality and homoscedasticity will be checked using statistical test and graphical methods (Residual and Q-Q plots, and Shapiro-Wilk tests) and transformation will be done as necessary. Restricted maximum likelihood methods will be used to estimate the fixed effects and variance components. Additional outcomes (e.g., PCL-5, CAPS-5 symptom subscales) will be examined.

Hypothesis 3A: Prefrontal cortex-amygdala connectivity at rest and in response to alcohol/drug vs. neutral cues will predict reduction in alcohol/substance use severity (total standard drinks).

Hypothesis 3B: Prefrontal cortex-amygdala connectivity at rest and in response to trauma vs. neutral cues will predict reduction in PTSD severity (CAPS-5).

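### The plan treats under 10% missing data as bias-free whatever the mechanism, switches to unspecified propensity-score imputation above 10%, and plans no missing-data sensitivity analysis

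*Combined protocol and SAP*

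**What the plan says.** Missing data are covered by two sentences in the Statistical Analyses paragraph. The first, introduced as a general statement, is that "less than 10% missing data have little impact on power and do not introduce bias, regardless of the missing data mechanism". The second is "If the percent missing data are greater than 10%, propensity score methods will be used for data imputation". The plan gives no propensity model, donor rule, role for treatment arm or number of imputations. It states no assumed mechanism, no expected dropout rate and no missing-data sensitivity analysis.

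The same paragraph says "Baseline characteristics found to be significantly associated with primary outcome measures will be included as covariates in the analyses", so baseline covariates can be missing too.

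The outcome analyses are mixed models. For Hypothesis 2, "generalized linear mixed effects regression models with a Gaussian distribution will be developed to assess group differences while adjusting for baseline CAPS-5 scores", and "Restricted maximum likelihood methods will be used to estimate the fixed effects and variance components". For Hypothesis 1 the plan specifies a mixed-effects framework: "A Poisson distribution will be assumed with a logarithm link function to assess the effects of NAC treatment", with hurdle models if zeros are in excess. It names no estimation method for Hypothesis 1, and does not say whether drinks are modelled by visit or as one total per participant. Hypothesis 3 uses linear regressions of change scores.

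In Table 1, the row "Clinician Administered PTSD Scale: CAPS-5" is marked at baseline, week 4, week 8 and the follow-ups. The row "PTSD Checklist: PCL-5" is marked at baseline, weekly from week 1, and at the follow-ups. The OCDS and TLFB are also weekly.

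**The concern.** No percentage of missing data guarantees absence of bias. What matters is how far the unseen values differ from what the model predicts for them, and whether that differs between arms. Five per cent missing can bias a treatment contrast, and 20% can leave it unbiased.

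The sentence also works as a rule. Below 10% it is the only thing the plan says about missing data, so uneven, outcome-related loss would be declared harmless in advance and not examined. Above 10%, a reader cannot tell what would be done or whether it would preserve the treatment contrast, and the variant could be chosen after the data are seen. With no expected dropout given, either branch may apply.

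CAPS-5 is the most exposed outcome, because only week 4 lies between baseline and the week 8 endpoint.

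**Working it through.** **The plan's own figure.** The 10% rule rests on no calculation in the documents, so there is nothing to reproduce. Each part can be tested.

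**Power.** Going from 90 to 81 participants (two-sided .05, equal arms) moves power from .967 to .950 at d = 0.8, and from .812 to .770 at d = 0.6. That part of the sentence is fair.

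**Inputs for bias.** From the documents: N = 90, alpha .05, and CAPS-5 at baseline, week 4 and week 8. Assumed:
- 1:1 allocation (45 per arm) and two-sided testing;
- 8 of 90 (8.9%) missing at week 8;
- unseen week 8 outcomes 0.5 to 1 SD worse;
- correlation with week 8 of .5 for baseline and .7 for week 4, and .5 between baseline and week 4.

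**Formula.** For a likelihood model using all visits to week 8:

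bias = (difference between arms in number missing / 45) × departure × share of week 8 not explained by earlier visits.

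R² of week 8 on baseline and week 4 = (.25 + .49 − 2 × .5 × .7 × .5) / (1 − .25) = .52, so the unexplained share is .48.

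The standard error of the adjusted difference is about .19 SD; with complete data it is √(2 × .75/45) = .183. Type I error is P(Z > 1.96 − bias/.19) + P(Z < −1.96 − bias/.19).

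| Split of the 8 losses | Bias at 0.5 SD | Bias at 1 SD | Type I error |
|---|---|---|---|
| 4:4, equal departures | 0 | 0 | 5.0% |
| 6:2 | 4/45 × .5 × .48 = .021 | .043 | 5.1 to 5.6% |
| 8:0 | 8/45 × .5 × .48 = .043 | .085 | 5.6 to 7.3% |

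Simulation of the likelihood estimator (8,000 runs per cell, Monte Carlo standard error about .0025) gave the same biases. Its rejection rates were .051 and .073 at 8:0, .055 and .052 at 6:2, and .051 and .048 at 4:4. At 6:2 the inflation is therefore barely distinguishable from none.

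**Sensitivity to the correlation.** With the last earlier visit correlated .5 with week 8, the unexplained share is .667 and the 8:0 bias .059 to .119 SD. At .85, nearer to a weekly measure, these are .270 and .024 to .048 SD.

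**Departure beyond what earlier visits predict.** The unexplained share becomes 1. At 8:0 the bias is 8/45 × .5 = .089 to 8/45 × 1 = .178 SD, with type I error 7.5 to 15.5% (simulated 7.5 and 14.9%). At 6:2 it is .044 to .089 SD, about 5.6 to 7.5%.

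**Is imputation needed under missing-at-random?** In a separate simulation (10,000 trials, all correlations .6, true difference zero, 8 of 90 missing in one arm depending on week 4), the likelihood estimate was −.003 SD with type I error .048, without imputation. Completer ANCOVA was biased by −.057 SD. What protects the contrast is using the earlier visits, not the 10% threshold.

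**The case against.** The strongest reply is that below 10% the wrong sentence changes little in practice. Its only operational effect is not to impute, and Hypothesis 2 is already a mixed model fitted by REML, which is also what this review recommends. That stands: what remains below 10% is a false rationale and no check on departures from missing-at-random.

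The larger errors also need one-sided loss. If dropout is unrelated to arm, all 8 losses falling in the same arm has probability 2 × C(45,8)/C(90,8) = .0056, about 0.6%. The trial is double-blind with matching placebo, both arms receive weekly CBT intended partly to aid retention, visits are paid, and telehealth participants are offered travel compensation for the week 4 and week 8 visits. OCDS and TLFB are weekly, and the TLFB is a retrospective calendar. All this stands and keeps the expected size modest.

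Two stronger readings are tempting.

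- A reader might infer that the above-10% imputation would dilute the treatment effect. In an illustrative propensity-quintile hot deck with donors pooled across arms (true d = 1.0), the effect shrinks by about 8 to 11% at 11% missing, 15 to 21% at 20% and 24 to 31% at 30%. The plan does not say that donors are pooled. Imputation within arm, equally consistent with the text, retained .992 to 1.014 of the effect. What the documents support is that the method is unspecified.
- A reader might infer that type I error would be far above 5%. Figures of 11 to 20% appear at 8.9% missing only if every loss is in one arm and selected on the unseen outcome. Nothing in the documents predicts that.

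Finally, the statement that imputation is not needed has a limit. If each participant contributes one drinks total, repeated-measures likelihood does not handle a partly observed total.

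**Conclusion.** The concern holds in a bounded form. The no-bias claim is false, the alternative above 10% cannot be reproduced from the text, and nothing in the plan tests departures from missing-at-random. Imputation is unnecessary for Hypothesis 1 and 2 outcomes only if they are modelled as repeated measures by likelihood, correctly specified, under missing-at-random. It can still have a use for missing baseline covariates and the Hypothesis 3 change scores.

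Under the stated assumptions the consequence runs from none, through slight at 6:2, to material only in the unlikely 8:0 extreme. The assumptions on allocation, correlations, departures and split set the size of the bias; they do not affect whether the sentence is wrong. The documents do not show that the trial's result will be biased or its effect diluted. The point is worth correcting because the correction is cheap and should be fixed before unblinding.

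**What to change.** Delete the no-bias sentence, and delete the 10% switch for Hypothesis 1 and 2 outcomes. State instead:

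- Hypotheses 1 and 2 are analysed by likelihood mixed models (REML for CAPS-5, maximum likelihood for the Hypothesis 1 models), using all observed on-treatment visits through week 8, under missing-at-random whatever the percentage missing.
- The target is the week 8 treatment contrast. Saying so keeps the 1- and 3-month follow-ups out of the primary model, since the hypotheses end at week 8.
- Drinks are modelled per visit interval, or with an offset for days observed.
- Where imputation is still needed (missing baseline covariates, Hypothesis 3 change scores), multiple imputation is used. Any imputed outcome that enters a treatment comparison is imputed separately by arm.
- One delta-adjusted sensitivity analysis is done for week 8 CAPS-5, with the shift varied by arm over a range of CAPS-5 points fixed before unblinding. Weekly PCL-5 may serve as an auxiliary variable.

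The cost is SAP wording and a little more analysis work. Trial conduct and data collection do not change.

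### The imaging power statement gives 26 as a total for d = 0.8, but 26 is the per-group number (52 in total); the matching clinical sentence does not say which it means

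*Combined protocol and SAP*

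**What the plan says.** All the relevant figures stand in one paragraph of the protocol, headed Power and Sample Size Estimation.

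- **Clinical sentence (PTSD symptoms and craving).** The paragraph gives d = 1.27 for PTSD and d = 1.03 for craving, which "respectively) are based on our PoP data". It continues: "A sample size of 26 would provide power" "of .80 to detect a large effect size", at a type 1 error of .05. It gives no numeric d for the large effect, no sidedness, and no indication of total or per arm.
- **AUD/SUD severity.** For this outcome "a total sample of 58 would be required", so here the figure is labelled a total.
- **Imaging, first figure.** "The effect size for this difference was 0.8", for a comparison of a PTSD group with controls in a published study. From this the paragraph concludes that power "reaches .80 with a total sample size of" 26, two-tailed, alpha .05. Both the d and the word total are explicit.
- **Imaging, second figure.** "The effect size for this reduction was 1.0", with 34 subjects for .80 power, two-tailed.

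Elsewhere, the Overview under METHODS plans 90 participants and the Neuroimaging Component plans a subset of 40. The allocation ratio is not stated.

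**The concern.** The same number, 26, is attached to .80 power in two sentences of one paragraph. In one it is explicitly a total for d = 0.8; in the other it is unlabelled and goes with an unquantified large effect. For a two-sample comparison at d = 0.8, 26 is a familiar per-group figure, so a per-group number appears to have been reported as a total.

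What is at stake differs between the two sentences. In the imaging sentence, a requirement of 26 makes the planned 40 look comfortably large, when on the sentence's own inputs 40 falls short of 80% power. In the clinical sentence, the figure is the only sample-size statement for two of the three primary clinical outcomes (CAPS-5 and OCDS), and a reader cannot tell whether 26 or 52 participants are meant.

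**Working it through.** **Inputs from the protocol.** d = 0.8 and 1.0 (imaging), d = 1.03 (craving), d = 1.27 (PTSD); alpha .05; power .80; two-tailed for imaging; 40 in the imaging subset; 90 in the trial.

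**Assumptions.** Two equal groups. Two-sided testing for the clinical outcomes, where sidedness is not given. d = 0.8 for the large effect in the clinical sentence, by the usual convention. No attrition and no covariate adjustment.

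**Formula.** With n per group, the two-sample t statistic has 2n − 2 degrees of freedom and noncentrality d√(n/2). Power is the probability that it exceeds the two-sided .05 critical value. The normal approximation for the size is n = 2(1.960 + 0.842)²/d² per group.

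**Step 1: where 26 comes from.** At d = 0.8 the approximation gives 2 × 7.85/0.64 = 24.5, so 25 per group. The noncentral t gives 25.5, so 26 per group, with power .81. The 26 is thus reproduced as a per-group number, and the total is 2 × 26 = 52.

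**Step 2: the imaging sentence as written.** A total of 26 is 13 per group. Noncentrality is 0.8 × √6.5 = 2.04, against a critical value of 2.06 on 24 degrees of freedom. Power is .50, not .80. The smallest d that 13 per group detects with .80 power is 1.15.

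**Step 3: the second imaging figure, for comparison.** At d = 1.0 the noncentral t gives 16.7, so 17 per group and 34 in total, with power .81. The paragraph's 34 is therefore correct as a total, which shows that the two imaging figures were not computed on the same footing.

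**Step 4: the planned imaging subset.** 40 split equally is 20 per group. Noncentrality is 0.8 × √10 = 2.53, against 2.02 on 38 degrees of freedom. Power is about .69. An unequal split, or exclusions for head motion, would lower it.

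**Step 5: the clinical sentence on each reading.**

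| d | Total needed for .80 | Power, 26 in total | Power, 26 per arm | Power, 90 in total |
|---|---|---|---|---|
| 0.8 (assumed) | 52 | .50 | .81 | .96 |
| 1.03 (craving) | 32 | .71 | .95 | .998 |
| 1.27 (PTSD) | 22 | .87 | .99 | >.999 |

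Read as 26 per arm at d = 0.8, the sentence is correct. Read as a total, 26 is too few for d = 0.8 and for craving at d = 1.03, but enough for PTSD at d = 1.27.

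**Step 6: variants for the clinical sentence read as a total.** A one-sided test gives .63 at d = 0.8 and .82 at d = 1.03. Adjustment for baseline with an assumed correlation of 0.5 gives .62 and .83 (two-sided). At d = 1.15, the mean of the two pilot effects, 26 in total gives .80.

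**The case against.** A reader might infer that the sample-size statement for PTSD and craving is itself wrong, because neighbouring figures are totals and the imaging sentence calls 26 a total for d = 0.8. The documents do not support that. The clinical sentence never says total, and its figure is reproduced as a per-arm number at d = 0.8. The labels around it cannot settle its meaning, since the imaging label does not fit its own number. Even as a total, 26 exceeds what PTSD needs at the plan's own d = 1.27. For craving the shortfall (.71) depends on a two-sided, unadjusted test: the sentence states no sidedness, and the analysis of Hypothesis 1 plans baseline craving as a covariate. This part of the objection stands, and it reduces the clinical point to a missing label.

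It can also be said that nothing turns on the clinical figure: 90 are planned, and the paragraph states a larger requirement of 58 for another outcome. That is fair as to consequence; whether 58 is sound is a separate question.

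Neither argument rescues the imaging sentence. There d, sidedness, alpha, power and the word total are all explicit. A one-sided test would still give only .63. A covariate would have to correlate with the outcome at more than 0.7 (power .78 at 0.7, .84 at 0.75), and the sentence mentions none.

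**Conclusion.** The imaging sentence contains a demonstrable error. At d = 0.8, two-tailed .05, a total of 26 gives power .50; 26 per group, 52 in total, is the requirement, half as much power again being missing is not recovered by the planned 40, which gives about .69. This rests on a two-group comparison with equal groups, the setting from which the sentence takes its effect size. Hypotheses 3A and 3B are tested by regression, for which this calculation does not speak directly.

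The clinical sentence is ambiguous and needs a label. It is not shown to be wrong, and it does not follow that the trial is underpowered for PTSD or craving: at 45 per arm (1:1 assumed) power is .96 at d = 0.8 and at least .99 at both pilot effects, before attrition. Nor do the documents show that the imaging slip was carried into the clinical sentence.

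**What to change.** 1. **Imaging sentence.** Give the requirement as 26 per group (52 in total) for d = 0.8, two-tailed, and add that the planned subset of 40 gives about .69 at 20 per group, before motion exclusions and dropout.
2. **Clinical sentence.** If the basis was d = 0.8, two-sided, label 26 as per arm (52 in total). If it was something else, state the d, the sidedness and the total used.
3. **Planned size.** Add that 90 participants (45 per arm if allocation is 1:1) give .96 at d = 0.8 and at least .99 at d = 1.03 and d = 1.27, before attrition.

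The cost is two or three sentences in one paragraph. The correction needs no change in enrolment, design or analysis.
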